a categorical variable), and treatment by time will be used to evaluate the mean difference in slope between sodium nitroprusside and placebo for the primary efficacy endpoint over 2 weeks. All time point data starting at the baseline measurement will be included in the analysis model, and treatment difference estimates at specific time points (e.g., Day 0, 7, 14, 21 and 28) will also be provided to assess the time course of effects.

Table of Contents

C.	Introduction and Background.....	9
D.	Study Rationale.....	11
E.	Objectives	11
F.	Study Design.....	11
G.	Study Population	17
H.	Study Assessments – Plan and Methods	20
I.	Treatment.....	42
J.	Ethical Considerations.....	46
K.	Data Handling and Record Keeping	47
L.	Monitoring and Oversight	48
M.	Data Analysis	50
N.	Publication Policy	57
O.	Protocol Signature Page	58
P.	Appendices	59
	Appendix 1: Schedule of Events.....	59
	Appendix 2: MGH- Fast Additive Summary of Treatment of Antipsychotic Medications	60
	Appendix 3: Concomitant Medications Allowed	63
	Appendix 4: Literature Cited	69
	Appendix 5: Study Scales	72

C. INTRODUCTION AND BACKGROUND

Statement of Intent

The design, conduct and reporting of this trial shall be conducted in accordance with the protocol, the United States 45 Code of Federal Regulations (CFR) part 46 known as “The Common Rule”, 45 CFR 164.502(d), and 164.514(a)-(c) known as “The Privacy Rule” of the Health Insurance Portability and Accountability Act (HIPAA), and the International Conference on Harmonization (ICH)/Good Clinical Practice (GCP). The data collection will also comply with 21 CFR part 11. All Investigators will have documented training in The Collaborative Institutional Training Initiative (CITI Program) in Biomedical Research and GCP. Independent monitoring of the trial will be conducted by a Contract Research Organization (CRO).

Background

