Indeed, initial studies with the nitric oxide donor nitroprusside completely attenuated behavioral effects of PCP in rats, a standard albeit limited rodent model of psychosis and antipsychotic action, and blocked PCP-induced c-fos expression in all brain regions without producing behavioral change when administered alone (Wang et al 2011). Nitroprusside also inhibited cocaine-induced immediate early gene expression in the frontal cortex and striatum (Thirlet et al. 2002). While the precise means by which NO donors may exert therapeutic effects remains unclear, these animal studies suggest that effects on NMDA signaling and/or modulation of excess corticostriatal dopamine may be relevant.

The recent report by Hallak et al. (Hallak 2013) of a positive placebo-controlled trial of nitroprusside infusion provides the first human data supporting the use of nitric oxide donors to achieve rapid, robust antipsychotic effect. Hallak and colleagues randomly assigned 20 symptomatic subjects with schizophrenia to a single 4 hour infusion of nitroprusside 0.5 μ g/kg/min or placebo and observed a large improvement of positive and negative symptoms (effect size of approximately 1.7) which achieved statistical significance at 2 hours and persisted for 28 days. Although high-dose nitroprusside may produce hypotension and cyanide toxicity, the investigators observed no side effects at the substantially lower doses used in their pilot study. This novel approach is supported by converging evidence from human genetics and animal models and represents a potential paradigm shift in the treatment of schizophrenia. If replicated, the potential impact on clinical care might include both emergency-room treatment of acute psychosis and office-based treatment of refractory symptoms. Once efficacy and safety are established, future studies can examine repeated administration for maintenance treatment while pursuing other agents targeting this pathway. Drugs acting on this pathway are currently in development for Alzheimer's disease (Lahti et al 1995).

Sodium Nitroprusside

Intravenous sodium nitroprusside was approved by the FDA in 1979 for management of hypertension and reduction of intra-operative blood loss; it releases nitric oxide by interacting with oxyhemoglobin, and thus represents a balanced arterial and venous vasodilator. It has been widely used clinically for related indications including exacerbation of congestive heart failure (Carlson 2013).

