This is a phase II proof of concept (POC), multi-center, prospective, randomized, placebo-controlled, Sequential Parallel Comparison Design (SPCD) study, in which a total of 60 subjects with schizophrenia will be randomized studywide.

The study will be conducted in two phases. The study treatment will be administered in a double-blind fashion for all subjects throughout both phases of the study. A total of 60 subjects with schizophrenia will be randomized in a 1:1:1 ratio to one of three treatment sequences: drug-drug, placebo-drug, or placebo-placebo. Subjects will be randomized directly following confirmation of eligibility (at completion of Visit 2). Subjects randomized to the drug-drug sequence (n=20) will receive i.v. sodium nitroprusside (0.5 µg/kg/min for 4 hours) at Day 0 and Day 14. Subjects randomized to the placebo-drug sequence (n=20) will receive i.v. placebo at Day 0 and i.v. sodium nitroprusside (0.5 µg/kg/min for 4 hours) at Day 14. Subjects randomized to the placebo-placebo sequence (n=20) will receive i.v. placebo at Day 0 and again at Day 14. The double-blind treatment will be divided into two phases: Phase 1 from Day 0 to Day 14, and Phase 2 from Day 14 through Day 28.

At the end of Phase 1 the randomized subjects will be assessed and categorized into responders and non-responders, based on 20% or more reduction in their PANSS total score between Visit 4 (Baseline, Day 0) and Visit 7(Day 14). The data from the subjects deemed placebo non-responders in Phase 1 who go on to either stay on placebo or to receive treatment with sodium nitroprusside will be pooled with the data from Phase 1 from all subjects, according to SPCD.

Figure 1 –

Nitroprusside SPCD Study Design

Efficacy analysis is based on results of the 10 groups in green boxes

[figure not shown]
[figure not shown]

Figure 2 – Study Schemata

Study Visit Overview

Screening

- Visit 1 (Screening Visit, Day -28 to -14): Consists of signing a HIPAA compliant informed consent form and study qualification based on evaluation of inclusion/exclusion criteria. Medical records will be requested from the participant's primary care physician for confirmation of relevant eligibility criteria.
- Visit 2 (Remote Independent Interview, Day -13 to -3): Consists of independent assessment to confirm the diagnosis and the appropriateness of the subject for the study. Eligibility will also be assessed at this visit by conducting a PANSS,

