- Incidence of Treatment-Emergent Adverse Events (TEAE)
- Incidence of withdrawals from the study due to TEAEs
- Percent change in Abnormal Involuntary Movement Scale (AIMS)
- Percent change in Systematic Assessment for Treatment Emergent Effects-Systematic Inquiry (SAFTEE-SI)
- Assessment of suicidality per the Columbia-Suicide Severity Rating Scale (C-SSRS)
- Changes in blood pressure and heart rate
- Changes in electrocardiogram (ECG) parameters

Sample Size Determination and Rationale

Sixty (60) subjects will be randomized in an effort to assure that 48 subjects complete the study.

The RCT Logic Calculator (by Schoenfeld, D and Ivanova,A; <http://www.rctlogic.com/calculator/calculator-continuous.aspx>) was used for this sample size calculation. This sample size will provide “sufficient” statistical power for the selected primary endpoint. The sample size calculation is based on the assumption that there is a clinically meaningful weighted (50%) average difference of 10 points (9 points in Stage 1 and 11 points in Stage 2) between sodium nitroprusside and placebo group accordingly, (with standard deviation of 14) in PANSS total scores after 2 weeks of treatment between the two treatment groups. This power calculation is based on a 20% attrition by Week 4 and 30% placebo response at the end of Stage 1. Under the above assumptions, 60 subjects will be required to meet the Type I error rate of 0.05 and an 81% power.

Randomization

This is a double-blind, placebo-controlled, multi-center, randomized clinical trial. Subjects who have provided written informed consent and have met all the inclusion criteria and have met none of the exclusion criteria will be randomized to one of the three treatment sequences.

The study design contains two double-blind treatment phases (i.e. Phase 1 and Phase 2) of the same duration of two weeks. Subjects will be randomly assigned using stratified block randomization. The randomization scheme will be programmed in to the CTMS software and will generate a randomization code for each subject upon enrollment into the study. Subjects will be stratified by primary treatment status (clozapine, versus antipsychotic other than clozapine) and by site. The number of subjects taking clozapine will be restricted to 20 study wide.

Blinding and prevention of Bias

All subjects, Investigators and their staff involved in the management of the study will be blinded to treatment assignments.

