For efficacy evaluation data points missing data will be imputed per the method that will be detailed in the SAP for the study.

Multiple Comparisons and Multiplicity

This is a two phase Sequential Parallel Comparison Design (SPCD) study.

A two-stage test (Weighted Z-test approach with fixed weight of 0.5 for each part of the study) will be used to combine the data on treatment effects from the two stages of the study. This method will address the Type I error rate adjustment to protect the trial wise Type I error at the final analysis.

For the primary endpoint there will be only one hypothesis testing and there will be no Type I error adjustment for testing this endpoint.

There will also be no Type I error adjustment on the hypotheses testing of the secondary endpoints, other than using the Closed Test procedure.

Statistical Methods

A Statistical Analysis Plan (SAP) will be developed and approved before the database is locked. The SAP will present the detailed statistical methodology to be used in analyzing the efficacy and safety data from this trial. Inferential statistics for all inferential statistical analysis will be based on a 2 sided test with Type I Error rate of 0.05.

All the efficacy endpoints presented here will be conducted using both the evaluable and ITT populations. All safety analysis will be conducted using the safety population.

All data collected will be summarized according to the variable type:

- Continuous data summaries will include:
 - Number of observations, mean, standard deviation, median, and minimum and maximum values.
 - Analysis of Covariance using the stratification factor for inferential statistics.
- Categorical data summaries will include:
 - Frequency counts and percentages.
 - Logit model will be used for inferential statistics using the stratification factors referenced.

Subject Disposition

The disposition of all subjects who sign an ICF will be provided. The numbers of subjects screened, randomized, re-randomized, completed, and discontinued during the study, as well as the reasons for all post-randomization discontinuations will be summarized by treatment group. Disposition and reason for study discontinuation will also be provided as a by-subject listing.

Demographics and baseline characteristics analysis

Demographics and baseline characteristics will be summarized by treatment group using appropriate descriptive statistics.

Concomitant Medications

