#### Clinical Laboratory Data

All laboratory values will be listed. Laboratory measurements will also be summarized as continuous variables and presented by treatment group and time point.

In addition, changes in vital signs, weight and ECG will be summarized over time.

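### The Synopsis reports two-group treatment differences at Days 21 and 28, but half of the placebo group is given nitroprusside at Day 14, so no two-group coding yields a clean drug-placebo time course after that day

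*Protocol*

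**What the plan says.** The Statistical Methodology entry of the protocol Synopsis describes a constrained longitudinal model with treatment group, time and their interaction, contrasting nitroprusside with placebo. On the data used: "All time point data starting at the baseline measurement will be included in the analysis model". On the output: "treatment difference estimates at specific time points (e.g., Day 0, 7, 14, 21 and 28) will also be provided", so as to describe how the effect develops over time. Table 4 (protocol Section M, repeated in the SAP) lists only two treatment groups.

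Protocol Section F randomises 60 subjects 1:1:1 to drug-drug, placebo-drug or placebo-placebo. "Subjects randomized to the placebo-drug sequence (n=20) will receive i.v. placebo at Day 0", and nitroprusside at Day 14. The drug-drug group receives a second nitroprusside infusion that day and the placebo-placebo group a second placebo infusion.

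Section M and the SAP mention neither this model nor Day 21 and Day 28 estimates. They specify MMRM or non-parametric methods under SPCD, with Stage 2 limited to placebo non-responders. The SAP's Clinical Laboratory Data section adds: "Laboratory measurements will also be summarized as continuous variables and presented by treatment group and time point".

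**The concern.** A two-level treatment term has a randomised meaning only until the second infusion. After that, subjects kept in their Phase 1 arm form a placebo group that is half treated. Subjects moved to their current treatment form a drug group that mixes one and two infusions and doubles in size at Day 14. The Synopsis does not say which coding applies, and neither gives a drug-placebo difference at Days 21 and 28 that continues the one at Days 7 and 14.

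Persistence is part of the reason for the trial. Protocol Section C cites a pilot study whose effect was one "which achieved statistical significance at 2 hours and persisted for 28 days". A curve that falls, stays level or rises after Day 14 because of the design could be read as evidence about how long the effect lasts.

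**Working it through.** **1. The plan's own figure.** Inputs from Section M: "weighted (50%) average difference of 10 points (9 points in Stage 1 and 11 points in Stage 2"; SD 14; 20% attrition by Week 4; 30% placebo response; inference "based on a 2 sided test with Type I Error rate of 0.05"; and the result "60 subjects will be required to meet the Type I error rate of 0.05 and an 81% power".

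- Stage 2 subjects per arm = 40 × 0.8 × 0.7 / 2 = 11.2 (the plan gives about 11).
- SE = √[0.25 × 14² × (1/20 + 1/40) + 0.25 × 14² × (2/11.2)] = √(3.675 + 8.75) = 3.525.
- Power = Φ(10/3.525 − 1.96) = Φ(0.877) = 0.81.

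The 81% reproduces. No all-subject Day 21 or Day 28 contrast enters it.

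**2. Groups kept by Phase 1 arm.** Measure effects as improvement over placebo-placebo at Days 21 and 28. Assume that the first infusion's 9 points persist in drug-drug, that the second infusion adds *a* points there, and that switched subjects gain *E* points.

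Contrast = (9 + a) − E/2.

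| E | a | Drug-drug v placebo-placebo | Two-group contrast | Share shown |
|---|---|---|---|---|
| 9 | 0 | 9 | 4.5 | 50% |
| 7.7 | 0 | 9 | 5.15 | 57% |
| 11 | 0 | 9 | 3.5 | 39% |
| 9 | 4.5 | 13.5 | 9.0 | 67% |
| 9 | 9 | 18 | 13.5 | 75% |

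Here E = 7.7 is 0.7 × 11, that is, the Stage 2 effect in the 70% who are non-responders and nothing in responders; E = 11 applies it to everyone. The values of *a* are assumptions, because the documents give none. A simulation of the first row gave 9.0, 9.0, 4.5 and 4.5 points at Days 7, 14, 21 and 28. Rows four and five look flat and rising against the 9 points at Day 14, yet both understate the two-infusion difference.

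The same 4.5 points also arise if the first infusion has worn off completely and the second gives a fresh 9 points in both sequences: 9 − 4.5 = 4.5. The contrast cannot tell this from a lasting effect.

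**3. Groups by current treatment.** The contrast is (9 + a + E)/2 in 40 v 20 subjects. With E = 9 and a = 0 it is 9, so nothing is halved. With a = 4.5 it is (13.5 + 9)/2 = 11.25, which is neither the one-infusion nor the two-infusion effect. Before Day 14 the groups were 20 v 40, so the curve joins different sets of subjects.

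**4. Precision (illustration only; the plan specifies no Day 28 test).** SE = 14 × √(1/n₁ + 1/n₂), which gives 4.43 for 20 v 20, 3.83 for 20 v 40, 4.95 for 16 v 16 and 4.29 for 16 v 32.

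- A 10-point effect has a chance of nominal significance of Φ(10/4.43 − 1.96) = 62% in drug-drug v placebo-placebo. Halved to 5 points in the two-group contrast it has Φ(5/3.83 − 1.96) = 26%. With 20% attrition the figures are about 52% and 21%.
- With the plan's Stage 1 effect of 9 points they are 53% v 22%, or 44% v 18% with attrition.

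**5. Last clean visit.** The Synopsis places the Visit 7 PANSS at Hours 3 to 4, and Section H places it between Hours 4 and 7. Either way it falls during or after the second infusion, and the pilot reported an effect by 2 hours. Visit 6 (Day 13) is therefore the last uncontaminated PANSS.

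**6. Laboratory data.** Visit 7 samples are taken at Hours −1 to 0, before the infusion. Only the Visit 9 samples follow the switch.

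**The case against.** A reader might infer that a lasting effect is certain to look halved. The documents do not support this. Halving needs three things: groups frozen by Phase 1 arm, an equal and lasting effect in switched subjects, and no added effect of the second drug-drug infusion. The first is the natural reading of a fixed group term but is not stated, and nothing in the documents establishes the other two.

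A reader might also infer that the primary analysis is damaged. It is not: Stage 2 compares placebo non-responders pre-randomised to drug or placebo, without this mixture.

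It can fairly be said that the sentence appears only in the Synopsis, that no durability endpoint or Day 28 hypothesis exists, and that Days 21 and 28 might be meant as Weeks 1 and 2 of Stage 2. The first two points limit the importance. The third is possible, but it is not what a model described as using all data from baseline with one treatment term says, and no later text supplies that reading.

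The laboratory part is narrow, since it reaches only Visit 9. Adverse events are summarised by stage as well as by treatment group.

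**Conclusion.** The point holds in a conditional form. As specified, the Day 21 and Day 28 estimates are not clean drug-placebo differences under either two-group coding. With Phase 1 coding they understate drug-drug v placebo-placebo whenever switched subjects benefit. With persistence and no added effect of the second infusion, 39% to 57% of a 9-point effect is retained, and exactly half if the switched subjects gain the same 9 points. If the second infusion adds benefit, the direction of the apparent trend is not predictable. With current-treatment coding the effect need not shrink, but one and two infusions are mixed and group membership changes at Day 14. The consequence is confined to supplementary time-course estimates and the Visit 9 laboratory summary.

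**What to change.** - Limit the two-group time course to data before the second infusion, that is, through Visit 6.
- For Days 21 and 28, report by the three randomised sequences: (a) drug-drug v placebo-placebo, labelled as the effect of the two-infusion course, and (b) placebo-drug v placebo-placebo measured from the Visit 6 baseline, labelled as the effect of one infusion. Use all randomised subjects and mark both as supplementary to the SPCD analysis.
- Present the Visit 9 laboratory summary by sequence.
- Put the same wording in the Synopsis and the SAP, since the SAP is now silent on this model.

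No new data are needed. The price is precision: 20 v 20 subjects, or about 16 v 16 after the stated attrition, instead of 20 v 40. Contrast (a) also does not isolate the persistence of a single infusion, because drug-drug subjects have had two by then. No randomised group receives one infusion at Day 0 and placebo at Day 14, so the design cannot estimate that directly beyond Visit 6, and the report should say so.

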Primary and Secondary Outcomes:	
The Structured Clinical Interview for DSM-IV-TR (SCID) will be used to confirm the diagnosis of schizophrenia.
 
An independent SAFER interview will confirm both diagnosis and severity of symptoms.
 
PANSS total, positive- and-negative subscale scores will be used to measure the primary outcomes. The PANSS will be collected at Visits 1, 2, 3, 4 (Hour 3 to 4), 5, 6, 7,

	
(Hour 3 to 4), 8 and 9.
 
The SAFTEE and the Abnormal Involuntary Movement Scale (AIMS), together with blood pressure and heart rate, will be used to assess the secondary outcomes of this study (safety and tolerability). AIMS and SAFTEE will be collected at Visits 3, 4, 6, 7 and 9.
 
The MATRICS Consensus Cognitive Battery (MCCB) is the standard tool for assessing cognitive change in trials of cognitive-enhancing agents in schizophrenia. The MCCB domains include: Speed of Processing; Attention/Vigilance; Working Memory; Verbal Learning; Visual Learning; Reasoning & Problem-Solving; and Social Cognition and the battery takes about 80 minutes to complete. The MCCB is accepted by the US FDA as a primary outcome measure for registry trials for cognition in schizophrenia. The MCCB composite score represents a global measure of cognition and is than outcome measure for inclusion in the efficacy analyses. MCCB will be collected at Visits 3, 6, and 9.
 
The University of California San Diego (UCSD) Performance-based Skills Assessment Brief (UPSA-B) (Mausbach et al., 2007). The UPSA-B will be administered Visits 3, 6, and 9. The UPSA-B consists of two of the five original UPSA domains, finances and communication, and has been shown to be highly correlated with the long form of the UPSA and to have substantial test-retest reliability (Green et al., 2011). Each subscale contributes 50 points; total scores range from 0 to 100 points with higher scores reflecting better performance. The UPSA-Brief requires approximately 10–15 minutes to complete and may be administered by a suitably trained lay professional.

Inclusion Criteria:	
Males and Females, 18-65 years of age, inclusive.
 
Meets Diagnostic and Statistical Manual of Mental Disorders Forth Edition (DSM-IV-TR) criteria for a primary diagnosis of Schizophrenia established by a structured psychiatric evaluation (SCID) based on DSM-IV-TR criteria.
 
Written informed consent in compliance with 21 CFR part 50 and in accordance with the International Conference

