Randomization: When all of the screening assessments, including the SAFER assessment, have been completed and entered into the CTMS, the subject's status will be moved to eligible and the CTMS will generate a randomization ID for the subject. This ID will be accessible to the site pharmacy and will be used to prepare the corresponding study treatment. Once a subject has been assigned a Randomization ID, they will be identified in the CRF by this Randomization ID for the duration of their study participation. The subject ID should no longer be used.

Phase 1

Visit 3 (Baseline, Day -2 to -1)

The following procedures will be conducted at Visit 3 for all subjects:

- Concomitant Medications
- Vital Signs
- Anthropometrics (height, weight, waist circumference, BMI)
- 12-Lead ECG
- Urine Drug Screen
- PANSS
- CGI-S
- CGI-I
- MATRICS
- UPSA-B
- AE/SAE Assessment
- AIMS
- SAFTEE-SI
- C-SSRS

Visit 4 (Phase 1 Study Treatment, Day 0)

Anthropometrics, vital signs, urinalysis, and concomitant medications will be collected for all subjects at the start of Visit 4 (Hours -1 to 0) prior to initiating the infusion. Subjects

will also have blood sample drawn for chemistry and electrolytes. Female subjects of childbearing potential will have a pregnancy test prior to the infusion. If pregnancy test is positive, subject will not continue with the infusion. Subjects who use tobacco will be provided transdermal nicotine in order to prevent withdrawal symptoms. The nicotine replacement will be based on the number of cigarettes per day (cpd) or tobacco equivalent collected at screening.

- ≥ 15 cpd: 21 mg patch
- 8-15 cpd: 14 mg patch
- 5-8 cpd: 7 mg patch
- <5 cpd: as needed nicotine gum or 2mg lozenges (1 piece every 3-4 hours)

Intravenous sodium nitroprusside or Placebo infusion will take place during Hours 0-4. Cardio-pulmonary monitoring will take place throughout intravenous infusion (see Infusion Monitoring and Discharge Procedures).

Following completion of infusion, the subject will have a post-infusion debrief. The following measurements will also be collected for all subjects between hours 4 and 7:

- Vital Signs
- 12-Lead ECG
- AE/SAE Assessment
- AIMS
- SAFTEE-SI
- PANSS
- CGI-S
- CGI-I

Following the completion of all study assessments, a study psychiatrist or nurse practitioner will perform discharge procedures in order release the subject at the end of the visit.

Visit 5 (Phase 1 Follow Up, Day 7)

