The following procedures will be conducted at Visit 5 for all subjects:

- Concomitant Medications
- Vital Signs
- Anthropometrics (weight, height, waist circumference, BMI)
- 12-Lead ECG
- PANSS
- CGI-S
- CGI-I

- AE/SAE Assessment
- C-SSRS

Phase 2

Visit 6 (Phase 2 Baseline, Day 13)

The following procedures will be conducted at Visit 6 for all subjects:

- Concomitant Medications
- Vital Signs
- Anthropometrics (weight, height, waist circumference, BMI)
- 12-Lead ECG
- Urine Drug Screen
- PANSS
- CGI-S
- CGI-I
- MATRICS
- UPSA-B
- AE/SAE Assessment
- AIMS
- SAFTEE-SI
- C-SSRS

Visit 7 (Phase 2 Infusion, Day 14)

Anthropometrics, vital signs urinalysis, and concomitant medications will be collected for all subjects at the start of Visit 7 (Hours -1 to 0) prior to initiating the infusion. Subjects will also have blood sample drawn for chemistry and electrolytes. Female subjects of childbearing potential will have a pregnancy test prior to the infusion. If pregnancy test is positive, subject will not continue with the infusion. Subjects who use tobacco will be provided transdermal nicotine in order to prevent withdrawal symptoms. The nicotine replacement will be based on the number of cigarettes per day (cpd) or tobacco equivalent collected at screening.

- ≥ 15 cpd: 21 mg patch
- 8-15 cpd: 14 mg patch
- 5-8 cpd: 7 mg patch
- < 5 cpd: PRN nicotine gum or lozenges 2 mg (1 piece every 3-4 hours)

Intravenous sodium nitroprusside or Placebo infusion will take place during hours 0-4. Cardio-pulmonary monitoring will take place throughout intravenous infusion (see Infusion Monitoring and Discharge Procedures).

Following completion of infusion, the subject will have a post-infusion debrief. The following measurements will be collected for all subjects between hours 4 and 7:

- Vital Signs
- 12-Lead ECG
- AE/SAE Assessment
- AIMS
- SAFTEE-SI
- PANSS
- CGI-S
- CGI-I

Following the completion of all study assessments, a study psychiatrist or nurse practitioner will perform discharge procedures in order release the subject at the end of the visit.

Visit 8 (Phase 2 Follow Up, Day 21)

The following procedures will be conducted at Visit 8 for all subjects:

- Concomitant Medications
- Vital Signs
- Anthropometrics (weight, height, waist circumference, BMI)
- 12-Lead ECG
- PANSS
- CGI-S
- CGI-I
- AE/SAE Assessment
- C-SSRS

Visit 9 (Phase 2 Final Follow Up/Study Completion, Day 28)

The following procedures will be conducted at Visit 9 for all subjects:

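### The Phase 1 responder rule uses PANSS ratings taken during or after the infusions, so Day 14 drug can decide who counts as a placebo non-responder

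*Protocol*

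**What the plan says.** Protocol section F sets the phase boundaries as "Phase 1 from Day 0 to Day 14, and Phase 2 from Day 14 through Day 28". On when the classification happens, it states: "At the end of Phase 1 the randomized subjects will be assessed and categorized into responders and non-responders". The criterion given for that split is a comparison of two infusion visits, "based on 20% or more reduction in their PANSS total score between Visit 4 (Baseline, Day 0) and Visit 7(Day 14").

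The PANSS times at those two visits are given in two places:

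- **Section B, Synopsis:** "The PANSS will be collected at Visits 1, 2, 3, 4 (Hour 3 to 4), 5, 6, 7", with the same Hour 3 to 4 window attached to Visit 7. That is inside the four-hour infusion.
- **Section H, Visit 4 and Visit 7:** PANSS appears in the post-infusion lists, introduced by "The following measurements will also be collected for all subjects between hours 4 and 7" and "The following measurements will be collected for all subjects between hours 4 and 7" respectively.

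The pre-infusion lists contain no PANSS. The Visit 7 list, for example, opens "Anthropometrics, vital signs urinalysis, and concomitant medications will be collected for all subjects at the start of Visit 7 (Hours -1 to 0") and goes on to blood samples and a pregnancy test.

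Elsewhere the baselines are different visits. Sections F and H label Visit 3 (Day -2 to -1) the Phase 1 baseline. Section H labels Visit 6 (Day 13) the Phase 2 baseline. Both visits include a PANSS, and each is required to fall the day before the infusion visit.

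The SAP does not settle the matter. Its Primary Efficacy Endpoint and Analysis Populations sections name no visits, and its Covariates section calls for baseline values without saying whose or when.

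**The concern.** SPCD relies on selecting the two Stage 2 arms by the same rule, applied to data that Stage 2 treatment cannot have touched. The surrounding text intends this: classification comes at the end of Phase 1, and the SAP refers to subjects who did not respond to placebo in Phase 1. The visits named in the rule do not deliver it.

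The sponsor's own rationale makes an early effect likely. Section C reports that the effect in the earlier placebo-controlled trial was one "which achieved statistical significance at 2 hours and persisted for 28 days", and section J says it was visible within four hours. A placebo-drug subject helped by the Day 14 infusion can therefore be recorded as a Phase 1 placebo responder and drop out of Stage 2. A matching placebo-placebo subject stays in.

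This contamination arises at Visit 7 and only in the placebo-drug sequence. Visit 4 is a separate problem: a score taken during or after the first infusion is not a baseline, and in the drug-drug sequence it would absorb early drug effect.

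**Working it through.** **Inputs from the plan** (Sample Size Determination; Analysis Populations; Multiple Comparisons): 20 per sequence, effects of 9 and 11 points, SD 14, 30% placebo response, 20% attrition, stage weights 0.5, two-sided 0.05, about 11 and 11 non-responders in Stage 2.

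**Assumed, because the documents do not say:**
- f, the share of the 11-point effect present at the Visit 7 rating: 0 to 1.
- r, the correlation of Stage 1 and Stage 2 changes: 0 to -0.5. The lower end is what equal, independent fluctuation around a stable level gives.
- Rating noise in the classifier: SD 4, range 0 to 8.

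**1. The plan's power reproduces.** Stage 2 n per arm = 20 × 0.8 × 0.7 = 11.2.

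SE1 = 14√(1/20 + 1/40) = 3.834. SE2 = 14√(2/11.2) = 5.916.

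Power = Φ(10 / [0.5√(3.834² + 5.916²)] − 1.96) = Φ(2.837 − 1.96) = 0.81, the stated 81%. This takes 70% non-response in both placebo sequences.

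**2. Size of the placebo-drug non-responder set.** n = 16 × Φ(q − 11f/s), with q = Φ⁻¹(0.70) = 0.5244 and s = √(14² + 4²) = 14.56.

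| f | q − 11f/s | share kept | n (placebo-drug) | n (placebo-placebo) |
|---|---|---|---|---|
| 0 | 0.524 | 0.700 | 11.2 | 11.2 |
| 0.25 | 0.336 | 0.631 | 10.1 | 11.2 |
| 0.5 | 0.147 | 0.558 | 8.9 | 11.2 |
| 1 | −0.231 | 0.409 | 6.5 | 11.2 |

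Over noise SD 0 to 8, n is 8.8 to 9.2 at f = 0.5 and 6.3 to 7.0 at f = 1. This loss does not depend on r.

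**3. Stage 2 difference with a constant effect.** Difference = 11 + r(m_PD − m_PP), where m = −(196/s) φ(a)/Φ(a) is the mean Stage 1 change among those kept, relative to the average placebo subject, and a is the second column above. At noise SD 4, m_PP = −6.69, and m_PD = −9.52 at f = 0.5 and −12.80 at f = 1.

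- r = 0: 11.0 and 11.0.
- r = −0.25: 11.7 and 12.5.
- r = −0.5: 11 + 0.5 × 2.83 = 12.4, and 11 + 0.5 × 6.11 = 14.05.

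**4. Simulated power** (40,000 trials per scenario; equal-weighted difference over its standard error). The reference rule is Visit 3 to Visit 6.

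| Scenario | Visit 3 to 6 rule | f = 0.5 | f = 1 |
|---|---|---|---|
| r = 0, constant effect | 79% | 76% | 70% |
| r = 0, effect SD 5 between subjects | n/a | 73% | 64% |
| r = 0, effect SD 8 between subjects | n/a | 69% | 55% |
| r = −0.25, constant effect | 80% | 79% | 76% |
| r = −0.5, constant effect | 83% | 84–85% | 84–85% |

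When the effect varies between subjects, the best responders to drug are the ones removed. The Stage 2 difference falls to 10.4 and 9.5 (SD 5) or 9.5 and 7.4 (SD 8) at f = 0.5 and 1.

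**5. Transient effect at Visit 7, no two-week effect.** Drug-favouring rejection, nominal 2.5%; the Visit 3 to 6 rule gives 2.7–2.9%:

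| Transient effect | r = 0 | r = −0.25 | r = −0.5 |
|---|---|---|---|
| 5.5 points | 3.0% | 3.6% | 4.4% |
| 11 points | 3.1% | 4.5% | 6.8% (5.8–7.2% over noise 0–8) |

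**6. Whether covariates rescue it.** At r = −0.5 with 11 points present at Visit 7:

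| Baseline adjusted for | Stage 2 difference under the 11-point effect | Rejection under the transient null |
|---|---|---|
| Visit 6 only | 12.1–13.1 | 4.1–5.3% |
| Visit 3 only | 14.5–14.9 | 7.4–8.2% |
| Both | 11.0 | 3.1–3.2% |

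The SAP does not say which it means.

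**The case against.** **Paired-visit errors.** The r = −0.5 figures treat the errors at Visits 4 and 7 as nearly those of Visits 3 and 6. If errors one day apart have correlation ρ, the effective correlation is −0.5ρ. A re-run with an 11-point acute effect and ρ = 0, 0.5 and 1 gave rejection of 3.0%, 4.7% and 7.3% under the transient null, and Stage 2 differences of 11.0, 12.7 and 14.3. This is fair. It moves the answer within the range r = 0 to −0.5 and means the r = −0.5 results are an upper end.

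**Choice of statistic.** The SAP speaks of a weighted Z-test, while the simulation uses a weighted difference. The weighted difference reproduces the planned 81%; averaging the two Z statistics does not (about 84%). With averaged Z at r = 0, power is 84%, 82% and 79% at f = 0, 0.5 and 1, so the loss is about 5 points instead of about 9. Rejection under the transient null at r = −0.5 is still 6.4%. The size changes but the problem does not.

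**Transient effect.** An acute effect that vanishes by two weeks runs against the persistence reported in sections C and J. True, but the trial exists to test that persistence.

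**Only a label slip.** The intent is clear, the SAP does not repeat the rule, and it promises further detail. However, the rule names two specific visits and no PANSS there is listed before the infusion, so following the text produces the fault. The Appendix 1 schedule is damaged in the available copy and the design figures are missing, so neither was relied on.

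**Conclusion.** The concern holds. As written, the rule lets the Day 14 infusion influence who is counted as a Phase 1 placebo non-responder, and it contradicts the baselines named elsewhere in the protocol. The planned sample size calculation itself is sound; what fails is its premise of equal non-response in the two placebo sequences.

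The imbalance in set size follows from any drug effect present at the Visit 7 rating. Its further consequence has no fixed direction. It may cost power (79% to 70% at worst for a constant effect with r = 0, more if effects vary), overstate the Stage 2 difference (up to about 14 against 11), or raise drug-favouring rejection under a transient effect. Those sizes rest on assumed values of f, r, noise and between-subject variation, and on the form of the test statistic. With no drug effect at that rating there is no harm. A reader of the results could not tell which case applied, so this must be corrected before the analysis.

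**What to change.** Before database lock and unblinding, replace the section F rule with:

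> Response is a fall of at least 20% in PANSS total score from Visit 3 (Phase 1 baseline) to Visit 6 (Day 13), using only ratings made before the Day 14 infusion.

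In the SAP, state that:
- the Phase 1 baseline is Visit 3;
- the Phase 1 endpoint and Phase 2 baseline are both Visit 6;
- the Phase 2 endpoint is Visit 9;
- the baseline covariates in each stage are listed by visit.

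Treat the Visit 4 and Visit 7 PANSS as acute post-infusion measures only. Reconcile their stated times (Hour 3 to 4 in the Synopsis, hours 4 to 7 in section H) and check Appendix 1 against them.

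**Cost:** wording and an analysis-set definition. The Visit 3, 6 and 9 ratings are already scheduled and sequences are assigned in advance, so no subject's treatment changes. The Phase 1 outcome moves from Day 14 to Day 13, although Visit 3 to Visit 6 still spans about two weeks. Adding a pre-infusion PANSS at Visits 4 and 7 would also work, but only for subjects not yet treated.
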